13.2. Classification

Any of the following events, and any death or hospitalization while on study, is to be reported to the sponsor immediately when investigator is aware. The sponsor may request additional information after the initial notification

13.2.1. Primary Adverse Event

A primary AE is one of the following events occurring within seven (7) days following an AF ablation procedure with the Circular IRE Catheter when used with IRE generator per protocol. Table 4 provides the PAEs and their descriptions.

A Clinical Events Committee (CEC) will be implemented to adjudicate the primary adverse events. The CEC will operate as described in the CEC Charter.

All reported Primary AEs will be monitored until they are adequately resolved or explained. The Clinical Events Committee (CEC) is to adjudicate the primary adverse events and operate following the regulations of the Committee.

Table 4: Primary adverse events and description/criteria

Primary AE	Description/ Criteria
Death (device or procedure related)	Subject death directly related to the device or procedure and occurs at any time during or after the procedure.
Atrio-Esophageal Fistula*	Is defined as a connection between the atrium and the lumen of the esophagus. Evidence supporting this diagnosis includes documentation of esophagus erosion combined with evidence of a fistulous connection to the atrium such as air emboli, an

	embolic event, or direct observation at the time of surgical repair. A CT or MRI scan is the most common method of documentation of an atrio-esophageal fistula.
Cardiac Tamponade**; ***/Perforation**	The development of a significant pericardial effusion during or within 30 days of undergoing an AF ablation procedure. A significant pericardial effusion is one which results in hemodynamic compromise, requires elective or urgent pericardiocentesis, or results in a 1 cm or more pericardial effusion as documented by echocardiography. Cardiac tamponade should also be classified as "early" or "late" depending on whether it is diagnosed during or following initial discharge from the hospital.
Myocardial Infarction	The presence of any one of the following criteria: 
 • Detection of ECG changes indicative of new ischemia (new ST-T changes or new LBBB) which persists for more than 1 h • Development of new pathological Q waves on an ECG, and • Imaging evidence of new loss of viable myocardium or new regional wall motion abnormality
Stroke/ Cerebrovascular Accident	Rapid onset of a focal or global neurological deficit with at least one of the following: change in level of consciousness, hemiplegia, hemiparesis, numbness, or sensory loss affecting one side of the body, dysphasia or aphasia, hemianopia, amaurosis fugax, or other neurological signs or symptoms consistent with stroke. 
Duration of a focal or global neurological deficit ≥ 24 h; or < 24 h, if therapeutic intervention(s) were performed (e.g., thrombolytic therapy or intracranial angioplasty); OR available neuroimaging documents a new hemorrhage or infarct; or the neurological deficit results in death.
 
No other readily identifiable non-stroke cause for the clinical presentation (e.g., brain tumor, trauma, infection, hypoglycemia, peripheral lesion, pharmacological influences)† Confirmation of the diagnosis by at least one of the following:
 
 • Neurology or neurosurgical specialist • Neuroimaging procedure (MR or CT scan or cerebral angiography) • Lumbar puncture (i.e., spinal fluid analysis diagnostic of intracranial hemorrhage) 
Stroke: (diagnosis as above, preferably with positive neuroimaging study)
 
 • Minor—Modified Rankin score < 2 at 30 and 90 days†† • Major—Modified Rankin score ≥ 2 at 30 and 90 days
Thromboembolism	Formation of a clot (thrombus) inside a blood vessel causing obstruction to blood flow. The thrombus can migrate (embolus) and obstruct distal vascular sites. Diagnostic tests to help detect thromboembolisms may include but are not limited to angiography (pulmonary or distal), ventilation-perfusion (V/Q) scans, venography, Doppler ultrasonography, spiral CT, and echocardiography. For the purposes of this study, silent

	(asymptomatic) cerebral embolism will not be considered a PAE.
Transient Ischemic Attack	New focal neurological deficit with rapid symptom resolution (usually 1 to 2 h), always within 24h. Neuroimaging without tissue injury.
Phrenic Nerve Injury / Diaphragmatic Paralysis	Absent phrenic nerve function as assessed by a sniff test. A phrenic nerve paralysis is considered to be permanent when not resolved at the final follow-up.
Heart Block	Impairment of AV conduction requiring intervention (e.g., temporary or permanent pacemaker) due to iatrogenic cause (e.g., inappropriate RF application, traumatic maneuvering of catheter or other intracardiac devices).
Pulmonary Vein Stenosis+	A reduction of the diameter of a PV or PV branch. PV stenosis can be categorized as mild <50%, moderate 50-70%, and severe 70% reduction in the diameter of the PV or PV branch. PV stenosis (> 70% PV narrowing) regardless of the presence or absence of symptoms and PV stenosis with \geq 50% PV narrowing when accompanied with relevant and related symptoms that cannot be explained by other etiologies will be considered a primary adverse event.
Pulmonary Edema (Respiratory Insufficiency)	Respiratory insufficiency resulting in pulmonary complications necessitating intubation or other significant intervention (including diuretics administered specifically for treating pulmonary edema or ICU hospitalization requiring oxygen administration but not intubation). Exclusion criteria include: 
• Pneumonia – infiltrate, fever and leukocytosis• Acute Respiratory Distress Syndrome
Vagal Nerve Injury/ Gastroparesis	Injury to the vagal nerve that results in esophageal dysmotility or gastroparesis. Vagal nerve injury is considered to be a major complication if it prolongs hospitalization++++, requires hospitalization, or results in ongoing symptoms for more than 30 days following an ablation procedure.
Pericarditis	Should be considered a major complication following ablation if it results in effusion which leads to hemodynamic compromise or requires pericardiocentesis, prolongs hospitalization++++ by more than 48 h, requires hospitalization++++, or persists for more than 30 days following the ablation procedure.
Major Vascular Access Complication / Bleeding	Major Bleeding: A major complication of AF ablation if it requires and/or treated with transfusion or results in a 20% or greater fall in HCT. Major Vascular Access Complication: Defined as hematoma, an AV fistula, or a pseudoaneurysm which requires intervention such as surgical repair or transfusion, prolongs the hospital stay, or requires hospital admission.

* Atrio-esophageal fistula that occurs greater than one week (7 days) post-procedure and up to 90 days post-procedure is considered and analyzed as a PAE.

** Cardiac Tamponade/Perforation occurring within 30 days of the AF ablation process will be considered Primary AEs

*** Hemodynamic compromise or instability is defined as Systolic BP < 80 mm Hg.

+ Pulmonary Vein Stenosis will be considered as a PAE if it occurs anytime during the 12- month follow up period.

† Subjects with non-focal global encephalopathy will not be reported as a stroke without unequivocal evidence based upon neuroimaging studies.

†† Modified Rankin score assessments should be made by certified individuals. +++++“Hospitalization” means the event necessitated an admission to a health care facility e.g., with at least an overnight stay. Emergency room visits that do not result in admission to the hospital should be evaluated for one of the other serious outcomes.

13.2.2. Serious AEs

A SAE is any AE that results in a death or a serious deterioration in the health of the subject during the clinical trial, including a life-threatening illness or injury, a permanent impairment of a body structure or a body function, in-patient hospitalization or prolongation of existing hospitalization*, medical or surgical intervention to prevent permanent impairment of a body structure or a body function; or results in fetal distress, foetal death or congenital abnormality, congenital anomaly, etc.

If it is a disease that exists before the scheduled hospitalization and/or medical intervention, or the operation required by the protocol but no serious deterioration in health, it will not be regarded as an SAE.

“Hospitalization” means the event necessitated an admission to a health care facility e.g., with at least an overnight stay. Emergency room visits that do not result in admission to the hospital should be evaluated for one of the other serious outcomes.

*Planned hospitalization for a condition present prior to the participant’s enrollment in the study will not meet the definition of an SAE but should nevertheless be included in routine study reporting.

13.2.3. Non-Serious AEs

A non-serious AE is any event that results in minimal transient impairment of a body function or damage to a body structure and does not require any intervention listed under the criteria for “Serious Adverse Event.” Non-serious adverse events require routine reporting via EDC.

13.2.4. Anticipated AEs

An anticipated AE is one that has been reported in previous studies of cardiac ablation and can be anticipated in this current study as per the risk analysis. Appendix II provides a comprehensive list of anticipated AEs. If listed then report event as anticipated.

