9.2. Possibility analysis on failure

Long term effectiveness is unknown for PFA technology. There is limited clinical data for this technology in cardiac ablation area. there may be some undetected problems that may result in some unforeseen results in this study.

Patients will be followed 3 times in clinic and 2 time by phone and have ECG and 24h Holter at 3M/6M/12M follow-ups, which is not SOC and would be challenging in following up.

10. Quality Control of Clinical Trial

During the clinical study, the sponsor and investigator should execute their respective responsibilities according to the *Good Clinical Practice for Medical Device Trials* and applicable relevant Chinese and international regulations. They should also strictly follow the clinical trial protocol, to ensure the quality of clinical trial.

The sponsor should, according to the requirements of the clinical trial protocol, organize the training on the clinical trial protocol and the use and maintenance of investigational product for all investigators participating in the trial, to ensure consistency in the implementation of clinical trial protocol and the use of

investigational products.

During the implementation of study, the sponsor is responsible for monitoring each phase of clinical trial. The clinical monitor designated by the sponsor or designated representative should comply with the relevant SOP and clinical trial protocol that are established by the sponsor to monitor the clinical trial, to ensure the complete, accurate, true, and reliable data.

To ensure the quality of study, the sponsor may authorize the qualified QC or auditor to audit the clinical trial as needed. The investigator should allow the auditors to access to the original data and documents related to this study after receiving the notification.

When the medical products administration or other health administrative authority appoints the inspection personnel to carry out inspection, the study sites and investigators should cooperate and immediately notify the sponsor.

11. Ethical Issues and Informed Consent of Clinical Trial

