13.2.5. Unanticipated Serious Adverse Device Effects

A (serious) adverse device effect (SADE) is any (serious) adverse effect on subjects' health, safety, rights, welfare, and life-threatening problems including death, which is caused by, or associated with the study device. Accordingly, relationship to device or study is a crucial assessment by investigators. An unanticipated adverse device effect (UADE) or unanticipated serious adverse device effect (USADE) is any ADE or SADE that has not been previously identified in nature, severity, or degree of incidence in the study plan or risk analysis report. An investigator shall submit to the reviewing EC a report of any unanticipated adverse device effect occurring during an investigation per EC requirements.

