Appendix II: ANTICIPATED ADVERSE EVENTS

(Acute) renal failure	Infection, systemic
(Aspiration) pneumonia	Inflammation
(Skin) laceration	Isolated ST segment elevation
(Vascular) bleeding	Liver toxicity
Acute Respiratory Distress Syndrome (ARDS)	Local Hematoma/ecchymosis
Air embolism	Localized skin reaction
Allergic reaction to contrast media Allergic skin reaction	Mitral Insufficiency
Allergic skin reaction	Myocardial infarction with or without ST elevation
Altered Mental Status Confusion; Altered Level of Consciousness;	Nausea
Anaphylactic shock	Neurological disorders (poor coordination)
Anemia	Neurological disorders (tremor)
Anesthesia complications/reactions	Neuropraxia/Muscle contraction
Anoxic or hypoxic encephalopathy	Palpitations
Aortic Puncture	Papillary Muscle tear/injury
Apnea - sedation induced	Pericardial effusion resulting in tamponade
Arrhythmia (new or worsening of pre-existing arrhythmia)	Pericardial effusion without tamponade
Asthmatic attack	Pericarditis
Asymptomatic Cerebral Emboli	Periesophageal vagal nerve injury
Atelectasis	Peripheral nerve injury
Atrial fibrillation	Phlebitis
Atrial Septal Defect (acquired)	Phrenic nerve damage/injury
Atrio-Esophageal fistula	Pleural effusion
Auditory Disorder	Pneumothorax
AV fistula	Post- and perioperative pain
Back Pain	Post Procedural Hematuria
Bone disorder	Pseudoaneurysm
Bronchial fistula, Broncho-pericardium fistula	Pulmonary edema
Cardiac arrest	Pulmonary embolism
Cardiac pacemaker insertion or replacement	Pulmonary hypertension
Cardiac perforation	Pulmonary toxicity, like acute pulmonary syndrome
Cardiac Valve Rupture/Damage	Pulmonary vein dissection
Cardiogenic Shock	Pulmonary vein stenosis
Cerebro-Vascular accident (CVA)/Stroke	Renal Artery Stenosis
Chest pain/discomfort	Respiratory arrest
Complete or incomplete heart block	Respiratory depression
Conduction block	Respiratory failure

Coronary Artery Stenosis	Respiratory infection
Coronary artery thrombosis	Retinal Artery Embolism
Death	Retroperitoneal bleeding
Deep venous thrombosis	Rhabdomyolysis, including produced by body position or propofol
Diaphragmatic paralysis	Sedation induced CO ₂ retention with lethargy and cholecystitis
Dislodgement/Malfunction of pacemaker/defibrillator leads	Seizure
Disseminated Intravascular Coagulation	Sepsis
Dizziness, presyncope, vertigo	Sinus bradycardia
Dysphagia	Sinus tachycardia
Dyspnea	Skin burn or necrosis
Endocarditis	Skin discoloration
Epigastric Distress	Skin edema

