Epistaxis	Skin or soft tissue (radiation) injury/tear
Esophageal injury / perforation	Subclavian artery puncture
Expressive aphasia	Temperature elevation / Fever
Fatigue	Thrombocytopenia
Gastric hypomotility	Thromboembolism
Gastroesophageal reflux	Thrombosis
Gastrointestinal disorders	Thyroid disorders
Gastrointestinal diverticulosis	Toxic reaction
Gastroparesis	Transient extremity numbness
Headache	Transient Ischemic attack (TIA)
Heart failure (acute or chronic)	Urinary Retention Postoperative
Heart injury	Urinary tract injury or infection related to the urinary catheter
Heart valve insufficiency	Valvular damage/insufficiency
Hemoptysis	Vascular (access) dissection (including coronary arteries)
Hemorrhage	Vascular occlusion
Hemothorax	Vasovagal reactions
High/increased creatine phosphokinase (CPK)	Ventricular Fibrillation
Hypertension	Vessel damage/trauma
Hypervolemia	Vessel perforation
Hypotension	Vessel spasm (including coronary arteries)
Hypovolemia	Visual disturbance
Hypoxia	Worsening of pre-existing pulmonary disease
Increased phosphokinase level	Wound healing disturbance

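### Protocol 13.2.4 labels listed events as anticipated by term alone, 13.2.5 also tests severity and incidence for device effects, and the protocol does not say which rule governs

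*Protocol*

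**What the plan says.** Protocol 13.2.4 first describes an anticipated AE as one that "has been reported in previous studies of cardiac ablation and can be anticipated in this current study as per the risk analysis". It then gives sites a working rule: "Appendix II provides a comprehensive list of anticipated AEs. If listed then report event as anticipated". That rule looks only at whether the term is on the list.

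Protocol 13.2.5 deals with adverse device effects. There an effect, serious or not, is unanticipated if it is one "that has not been previously identified in nature, severity, or degree of incidence in the study plan or risk analysis report". The section attaches a duty to that status: "An investigator shall submit to the reviewing EC a report of any unanticipated adverse device effect occurring during an investigation per EC requirements".

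Appendix II is a two-column list of terms with no severity grade, expected frequency or time limit. It contains specific events such as "Atrio-Esophageal fistula", broad groups such as "Gastrointestinal disorders", and the outcome *Death*.

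SAP 3.3.1 uses the label in three outputs: the overall AE summary, a table of unanticipated AEs by system organ class, preferred term and relationship (procedure, catheter, generator), and the by-subject AE listing. The SAP does not define unanticipated.

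**The concern.** Two adjacent sections give different tests for the same label. A site following 13.2.4 stops once it finds the term in Appendix II. A site following 13.2.5 must also ask whether the severity or frequency goes beyond what was foreseen. The protocol does not rank the rules, and neither section says who judges frequency, which one site cannot see across the study.

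The label matters more than usual here. Protocol 3.3 says the devices are not registered in any other country. The human experience with the system described in 3.2.2 is a 40-subject first phase of an ongoing study. Section 9.2, although a feasibility paragraph that opens with long-term effectiveness, calls clinical data limited and says "there may be some undetected problems that may result in some unforeseen results in this study". A table of unanticipated events is where a reader of the final report would look for new risks. If site labels follow the term-only rule, that table can understate them.

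**Working it through.** No formula applies and the plan states no figure to reproduce. The check has three steps.

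**1. Does Appendix II cover the primary adverse events?** Appendix II has 71 two-column rows, so 71 × 2 = 142 entries. Each Table 4 category was matched to it:

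| Table 4 category | Appendix II term |
|---|---|
| Death (device or procedure related) | Death |
| Atrio-esophageal fistula | same term |
| Tamponade / perforation | effusion with tamponade; cardiac perforation |
| Myocardial infarction | same, with or without ST elevation |
| Stroke / CVA | same term |
| Thromboembolism | same term |
| TIA | same term |
| Phrenic injury / diaphragmatic paralysis | both listed |
| Heart block | complete or incomplete |
| Pulmonary vein stenosis | same term |
| Pulmonary edema | same term |
| Vagal injury / gastroparesis | both listed |
| Pericarditis | same term |
| Major vascular access complication / bleeding | components only: vascular bleeding, AV fistula, pseudoaneurysm, local hematoma |

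Result: 14 of 14 are covered, 13 by the same or nearly the same name and 1 through components. Read literally, 13.2.4 labels every primary adverse event as anticipated.

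**2. When do the two rules disagree?**

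| Event | 13.2.4 | 13.2.5 | Conflict? |
|---|---|---|---|
| Listed, not a device effect | anticipated | does not apply | no |
| Listed device effect, as foreseen | anticipated | not unanticipated | no |
| Listed device effect, worse or more frequent than foreseen | anticipated | unanticipated | **yes** |
| Device effect not listed | not made anticipated by the list | tested against study plan and risk analysis | no |

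The conflict is confined to the third row. Being listed in the study plan can settle the kind of event. It cannot settle severity or frequency, because Appendix II states neither.

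**3. What depends on the label?**

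- Dependent: the investigator's EC report in 13.2.5, and the three SAP outputs.
- Not dependent: reporting of every SAE to the site's trial department, the sponsor and the EC within 24 hours (13.5); sponsor reports of device-associated SAEs within 7 or 15 days (13.5); expedited reporting of deaths from any cause (13.2.6, Table 6); immediate notice to the sponsor of primary adverse events, deaths and hospitalizations (13.2); and Clinical Events Committee adjudication of primary adverse events (13.2.1).

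A serious event in the third row therefore still reaches the EC, but may arrive without the unanticipated flag. A non-serious one goes to the sponsor through the e-CRF within 2 weeks (13.2.3, 13.5). Its only EC route in these sections is 13.2.5, which a site relying on 13.2.4 may not use.

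**The case against.** The best reply is that 13.2.4 sets a label and does not switch off 13.2.5. The EC duty in 13.2.5 rests on its own definition and never mentions Appendix II. This stands. A reader might infer that unanticipated device effects are suppressed, and the documents do not support that. They show two rules without a stated order, and serious events are reported and adjudicated whatever the label.

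Second, the remaining gap for EC reporting is narrow. The event must be device-related, listed, beyond what was foreseen, and still non-serious. Since 13.2.3 limits non-serious events to minor, transient impairment or to damage needing no SAE-type intervention, an event of markedly greater severity would usually become an SAE. This also stands. It bears less on frequency, because a cluster of mild events can exceed expectation without any one of them being serious.

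Third, a reader might infer that the unanticipated-AE table will be near zero by construction. That does not follow. Any AE outside Appendix II can still enter it, and no event rates are available to size the shortfall. An undercount is the most that can be said.

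Fourth, listing *Death* might suggest that a device-related death of any mechanism has to be called anticipated. Table 6 treats a fatal result as the outcome of an underlying AE, the SAP summarises cause of death, and 13.2.5 includes death among device effects, so a death can be entered under its cause. The literal wording of 13.2.4 still leaves the other choice open.

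Finally, the definition in 13.2.4 does refer to the risk analysis. Its last sentence drops that condition, and the last sentence is the instruction sites follow.

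**Conclusion.** The conflict is real and limited. For listed, device-related events that exceed the foreseen severity or incidence, 13.2.4 and 13.2.5 give different labels and must be reconciled. The scope of the list is wide: about 142 terms, with all 14 primary adverse event categories covered.

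The supportable consequences are misclassification at site level, an undercount of unknown size in the SAP's unanticipated-AE outputs, SAEs reaching the EC without the flag, and possible loss of the EC report for some non-serious device effects. No primary endpoint, sample size or decision rule is affected.

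The conclusion assumes that sites apply the last sentence of 13.2.4 as written. The risk analysis report and the Safety Events Management Plan are not among the documents. They may hold severity or incidence benchmarks, or a sponsor re-flagging step, which would reduce the practical effect. They would not remove the contradiction in the protocol text.

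**What to change.** Make three wording changes in the protocol and the CRF guidance:

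1. Replace the last sentence of 13.2.4 with: *A listed device-related event is reported as anticipated only if its nature and severity are consistent with the risk analysis; otherwise it is classified under 13.2.5.*
2. State that the sponsor judges degree of incidence across the whole study and re-flags events where needed.
3. State that a death is classified by its underlying cause and not by the listed term *Death*.

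Replacing the broad terms in Appendix II with specific events is optional and is not needed to resolve the conflict. The SAP's tables can stay as specified, since they would then rest on a consistent flag. The cost is that a few more events will be flagged and reviewed as unanticipated. Design, sample size and treatment are unchanged.
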